BSA = body surface area; CBC = complete blood count; DNA = deoxyribonucleic acid; ECG = electrocardiogram; eC-SSRS = electronic Columbia Suicide Severity Rating Scale; FSH = follicle stimulating hormone; HBV = hepatitis B virus; HBcAb = hepatitis B core antibody; HBsAb = hepatitis B surface antibody; HBsAg = hepatitis B surface antigen; HCV = hepatitis C virus; HIV = human immunodeficiency virus; hs-CRP = high-sensitivity C-reactive protein; IRT = interactive response technology; PASE = psoriatic arthritis screening and evaluation; PASI = Psoriasis Area and Severity Index; PE = physical examination; PHQ-8 = eight-item Patient Health Questionnaire; PsA = psoriatic arthritis; PSSD = Psoriasis Symptoms and Signs Diary; SAE = serious adverse event; sPGA = static Physician Global Assessment; T3 = triiodothyronine; T4 = thyroxine; TB = tuberculosis; TSH = thyroid stimulating hormone; V = visit; WOCP = women of childbearing potential.

Table 2: On-Treatment Procedural Outline (IM011065): Week 0 through Week 20

Procedure	Week 0 Baseline / D1 V2	Week 1 D8 (±3 d) V3	Week 2 D15 (±3 d) V4	Week 4 D29 (±3 d) V5	Week 8 D57 (±3 d) V6	Week 12 D85 (±3 d) V7	Week 16 D113 (±3 d) V8	Week 20 D141 (±3 d) V9	Notes
Clinical Efficacy/Health Outcomes									
DLQI	X	X	X	X	X	X	X		
sPGA	X	X	X	X	X	X	X		
PASI	X	X	X	X	X	X	X		
ss-PGA ^a	X	X	X	X	X	X			
PGA-F ^b	X			X	X	X			
Palmoplantar PGA ^c	X	X	X	X	X	X			

Table 2: On-Treatment Procedural Outline (IM011065): Week 0 through Week 20

Procedure	Week 0 Baseline / D1 V2	Week 1 D8 (±3 d) V3	Week 2 D15 (±3 d) V4	Week 4 D29 (±3 d) V5	Week 8 D57 (±3 d) V6	Week 12 D85 (±3 d) V7	Week 16 D113 (±3 d) V8	Week 20 D141 (±3 d) V9	Notes
PSSD									
Safety Assessments									
Complete PE	X						X		
Targeted PE		X	X	X	X	X		X	See Section 8.4.1
Body Weight	X						X		
Vital Signs	X	X	X	X	X	X	X	X	
ECG	X						X		
PHQ-8	X				X		X		See Section 8.4.6.1
eC-SSRS Assessment	X				X		X		Suicidal Ideation and Behavior since last visit
Adverse Event Assessment	X	X	X	X	X	X	X	X	
Concomitant Medication Use	X	X	X	X	X	X	X	X	
Laboratory Tests									
Hematology	X	X	X	X	X	X	X	X	
Lymphocytes Subsets (TBNK)	X				X		X		
Chemistry Panel	X	X	X	X	X	X	X	X	If CK >2.5 × ULN, reflex testing is required (see Section 8.4.5)
Hemoglobin A1C	X						X		
hs-CRP	X	X	X	X	X		X	X	

Table 2: On-Treatment Procedural Outline (IM011065): Week 0 through Week 20

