Procedure	Week 24 D169 (±3 d) V10	Week 28 D197 (±3 d) V11	Week 32 D225 (±3 d) V12	Week 36 D253 (±3 d) V13	Week 40 D281 (±3 d) V14	Week 44 D309 (±3 d) V15	Week 48 D337 (±3 d) V16	Week 52 ^a (or early DC) D365 (±3 d) V17	Safety Follow-up ^b (Week 56) D393 (±3 d) V18	Notes
Safety Assessments										
Full PE	X							X	X	
Targeted Physical Examination		X	X	X	X	X	X			
Body Weight								X	X	
Vital Signs	X	X	X	X	X	X	X	X	X	
ECG	X							X		
PHQ-8		X			X			X		See Section 8.4.6.1
eC-SSRS		X			X			X		Suicidal Ideation and Behavior since last visit
Adverse Event Assessment	X	X	X	X	X	X	X	X	X	

Table 3: On-Treatment Procedural Outline (IM011065): Week 24 through Week 52

Procedure	Week 24 D169 (±3 d) V10	Week 28 D197 (±3 d) V11	Week 32 D225 (±3 d) V12	Week 36 D253 (±3 d) V13	Week 40 D281 (±3 d) V14	Week 44 D309 (±3 d) V15	Week 48 D337 (±3 d) V16	Week 52 ^a (or early DC) D365 (±3 d) V17	Safety Follow-up ^b (Week 56) D393 (±3 d) V18	Notes
Concomitant Medication Use	X	X	X	X	X	X	X	X	X	
Laboratory Tests										
Hematology	X	X	X	X	X	X	X	X	X	
Lymphocytes Subsets (TBNK)				X				X		
Chemistry Panel	X	X	X	X	X	X	X	X	X	If CPK >2.5 × ULN, reflex testing is required (see Section 8.4.5)
Fasting Lipid Panel	X							X		Subjects are required to fast for at least 10 hours prior to collection
Fasting Plasma Glucose	X							X		
hs-CRP	X			X				X		
Hemoglobin A1C				X				X		
Urinalysis				X				X	X	
Serum Immunoglobulin Levels (IgM, IgG, IgA, IgE)				X				X		

Table 3: On-Treatment Procedural Outline (IM011065): Week 24 through Week 52

Procedure	Week 24 D169 (±3 d) V10	Week 28 D197 (±3 d) V11	Week 32 D225 (±3 d) V12	Week 36 D253 (±3 d) V13	Week 40 D281 (±3 d) V14	Week 44 D309 (±3 d) V15	Week 48 D337 (±3 d) V16	Week 52 ^a (or early DC) D365 (±3 d) V17	Safety Follow-up ^b (Week 56) D393 (±3 d) V18	Notes
Pregnancy Test (Urine)	X	X	X	X	X	X	X	X	X	WOCBP Only
Study Treatment										
Dispense Study Treatment	X	X	X	X	X	X	X			
Study Treatment Compliance	X	X	X	X	X	X	X	X		

BMI = body mass index; eC-SSRS = electronic Columbia-Suicide Severity Rating Scale; CK = creatine kinase;

ECG = electrocardiogram;

hs-CRP = high-sensitivity C-reactive protein; Ig = immunoglobulin;

PE = physical examination;

PHQ-8 = eight-item Patient Health Questionnaire;

ULN = upper limit of normal; TBNK = T, B, and natural killer cells;

Wk = Week; WOCBP = women of childbearing potential

^a For subjects who discontinue from the study prior to Week 52, all Week 52 Visit assessments are to be performed.

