BMS reserves the right to terminate access to BMS supplied study treatment if any of the following occur: a) the study is terminated due to safety concerns; b) the development of BMS-986165 is terminated for other reasons, including but not limited to lack of efficacy and/or not meeting the study objectives; c) the subject can obtain medication from a government sponsored or private health program. In all cases BMS will follow local regulations.

7 *DISCONTINUATION CRITERIA*

7.1 *Discontinuation from Study Treatment*

Subjects MUST discontinue IP (and non-IP at the discretion of the investigator) for any of the following reasons:

- Subject requests to stop study treatment. Subjects who request to discontinue study treatment will remain in the study and must continue to be followed for protocol-specified follow-up procedures. The only exception to this is when a subject specifically withdraws consent for any further contact with him/her or persons previously authorized by subject to provide this information.
- Any clinically significant AE, laboratory abnormality, or intercurrent illness which, in the opinion of the investigator, indicates that continued participation in the study is not in the best interest of the subject. If treatment is discontinued due to an AE, the AE eCRF must be completed to show that the AE caused discontinuation
- eGFR <45 mL/min on repeat assessment within 7 days
- Abnormal liver tests suggestive of drug-induced liver injury (DILI), as defined in [Section 8.2.8](#) or if the investigator believes that it is in the best interest of the subject
- Subject reports suicidal ideation, suicidal behavior, or suicide attempts at any time after randomization, or documents suicidal ideation by answering "Yes" to Question 4 or 5 on the eC-SSRS, or documents suicidal behavior on the eC-SSRS at any time during the study. The subject should then be immediately referred to a mental health professional for evaluation of suicide risk.

- The subject develops a malignancy with the exception of a subject who develops nonmelanoma skin cancer who may continue in the study at the discretion of the investigator.
- Pregnancy, positive pregnancy test or subject expresses an interest in becoming pregnant (refer to [Section 8.2.6](#))
- Subject develops active TB during the study or prematurely discontinues treatment for LTBI, or subject is noncompliant with LTBI therapy (refer to [Section 8.4.4](#))
- Termination of the study or program by BMS

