In cases where the QT interval corrected using Bazett's (QTcB) formula is captured instead of QTcF, then the uncorrected QT will be converted to QTcF for analyses.

- Eight-Item Patient Health Questionnaire (PHQ-8) total score
 - Absolute and change from baseline values
 - Shifts from baseline scores
- Electronic Columbia-Suicide Severity Rating Scale (eC-SSRS)
 - Suicidal ideation and suicidal behavior responses by visit
 - Shifts from baseline to postbaseline value for suicidal ideation and suicidal behavior
 - Worst postbaseline value for suicidal ideation and behavior

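### The eC-SSRS recall is set to the last visit, not the last eC-SSRS; read literally, 32 of 52 treatment weeks fall outside the instrument's recall

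*Protocol*

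**What the plan says.** **Schedule.** In protocol Section 1.3, the Table 2 row labelled "eC-SSRS Assessment" is marked at Weeks 0, 8 and 16. The matching row in Table 3 is marked at Weeks 28, 40 and 52. Both rows carry the same note on the reference period: "Suicidal Ideation and Behavior since last visit". Scheduled visits without an eC-SSRS fall at Weeks 1, 2, 4, 12, 20, 24, 32, 36, 44 and 48.

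**Meaning of visit.** Every column of the schedule is a numbered visit. The Week 28 assessment is in the column headed "Week 28 D197 (±3 d) V11". The column before it is "Week 24 D169 (±3 d) V10", which has no eC-SSRS.

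**Other text.** Section 8.4.7 refers back to the schedule for timing and gives no recall period. Appendix 22 mentions an assessment period in its category definitions but does not define it. SAP Section 8.2.2.10 lists the categories without a recall period.

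**Use of the data.** Section 7.1 makes certain suicidality findings reasons to stop study treatment, and its eC-SSRS behavior limb reads "or documents suicidal behavior on the eC-SSRS at any time during the study". SAP Section 4.2 lists "Worst postbaseline value for suicidal ideation and behavior" as a safety outcome. SAP Section 6.2.6.2 adds positive responses by time point and shifts from baseline to the maximum postbaseline response.

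**The concern.** An instrument given at only some visits has unbroken coverage only if each administration looks back to the previous administration. Here the note points to the last visit, and before every post-baseline eC-SSRS the last visit is one at which the instrument was not given. Take suicidal behavior at Week 18. The subject attends Weeks 20 and 24 without an eC-SSRS and at Week 28 is asked about the time since Week 24. A truthful answer is no.

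Two things are at stake. The eC-SSRS limb of Section 7.1 is meant to work at any time in the study, but under this recall it can act only on events in the covered weeks. The SAP's worst postbaseline value would also be a maximum over those weeks alone, and a reader of the safety tables could not tell. Suicidal ideation and behavior has its own adjudication committee (Section 4.1.6.4), so the reference period of its structured measure should not be left to interpretation.

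**Working it through.** The documents state no coverage figure, so there is none to reproduce. The check is an interval count.

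**Inputs (protocol Section 1.3, Tables 2 and 3).** Visits at Weeks 0, 1, 2, 4, 8, 12, 16, 20, 24, 28, 32, 36, 40, 44, 48 and 52. eC-SSRS at Weeks 0, 8, 16, 28, 40 and 52. Treatment lasts 52 weeks (Section 4.1). Week 0 looks back into screening and covers no treatment week, so five assessments do the covering.

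**Formula.** Weeks covered = sum over post-baseline eC-SSRS visits of (week of assessment − week of the visit the recall starts from).

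| eC-SSRS at | Preceding visit | Covered, literal reading | Not covered, literal reading | Covered if recall starts at last eC-SSRS |
|---|---|---|---|---|
| Week 8 | Week 4 ("Week 4 D29 (±3 d) V5") | 4 | Weeks 0–4: 4 | 8 |
| Week 16 | Week 12 ("Week 12 D85 (±3 d) V7") | 4 | Weeks 8–12: 4 | 8 |
| Week 28 | Week 24 | 4 | Weeks 16–24: 8 | 12 |
| Week 40 | Week 36 | 4 | Weeks 28–36: 8 | 12 |
| Week 52 | Week 48 | 4 | Weeks 40–48: 8 | 12 |
| Total | | **20** | **32** | **52** |

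**Literal reading.** 20/52 = 38% covered; 32/52 = 62% not covered. In days, 5 × 28 = 140 of 364 are covered and 224 are not.

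**By period.** Weeks 0–16: 4 + 4 = 8 of 16 not covered. Weeks 16–52: 8 + 8 + 8 = 24 of 36 not covered. For subjects switched from placebo, Weeks 16–24 are their first 8 weeks on BMS-986165.

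**Visit windows.** With ±3 days at each end, a 28-day interval can run from 22 to 34 days, so five intervals cover 110 to 170 days. With total time held at 364 days, the uncovered time is (364 − 170)/7 = 27.7 to (364 − 110)/7 = 36.3 weeks. Visit timing does not remove the gap.

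**Alternative reading.** If the last visit means the last eC-SSRS visit, 8 + 8 + 12 + 12 + 12 = 52 weeks are covered and the gap is 0.

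**Follow-up.** No eC-SSRS is marked at Week 56. For subjects who do not roll over, the literal gap to Week 56 is 56 − 20 = 36 weeks. On the alternative reading it is 56 − 52 = 4 weeks.

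**Does the PHQ-8 fill the gap?** No. It is given at the same on-study visits, and none of its eight items (Appendix 21) asks about suicidality.

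**The case against.** The strongest objection is that the note sits in the eC-SSRS row and may simply mean since that instrument was last given. The gap is then zero. The eC-SSRS is also computer-automated and self-reported (Section 8.4.7.1), so what subjects are asked depends on the device, whose wording the documents do not show. This stands as a limit on the finding: a reader might infer that subjects were in fact not asked about 32 weeks, and the documents cannot show that. It does not remove the defect. Visits are numbered throughout the schedule, nothing defines the term otherwise, and the two readings differ by 32 weeks of structured ascertainment.

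The second objection is that a reader might infer that suicidality goes unmonitored between assessments. The documents do not support that. Section 7.1 also acts on a subject's own report at any time after randomization. Section 8.4.7 has family or caregivers told to report immediately. Adverse events are assessed at every visit, and Section 8.2.2 has SAE monitoring at every visit. In the Week 18 example, the subject has adverse event assessments at Weeks 20, 24 and 28. This objection is right on scope. These routes are unstructured, however: Section 8.2.3 keeps adverse event questioning open-ended and rules out asking about specific events, so none of them replaces the scale.

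Third, a reader might infer that the SAP presents its worst postbaseline value as covering the whole period. It does not say so. The value is a maximum of observed responses, and no eC-SSRS rate per unit of follow-up is specified. The narrower point remains that, on the literal recall, the maximum is taken over 20 weeks and the SAP does not tell the reader so.

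**Conclusion.** The point holds as a wording defect in a safety schedule. As written, the five post-baseline assessments cover 20 of 52 treatment weeks and leave 32 (62%) outside the instrument's recall: 8 of 16 in the placebo-controlled period and 24 of 36 afterwards. Weeks 0 to 4 and Weeks 16 to 24 are among those missed.

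The size rests on one assumption, that the last visit means the preceding numbered visit. The range is 0 weeks if the last eC-SSRS was intended, and 32 weeks at nominal timing (27.7 to 36.3 with visit windows at their extremes) if the note is followed literally. The documents do not settle which applies.

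The consequence is limited to the structured instrument, the eC-SSRS limb of the Section 7.1 rule and the SAP's worst-value and shift summaries. The other reporting routes still operate. No coprimary or key secondary endpoint is affected. The correction should be made because the measure concerns a serious, adjudicated risk and clarifying it costs little on either reading.

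**What to change.** In the Notes column of the eC-SSRS rows in Tables 2 and 3, define the recall as running from the last completed eC-SSRS assessment. Confirm that the device uses, and preferably displays, that date. Tying the recall to the last completed assessment also covers a missed one.

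With the same six assessments, the nominal gap over Weeks 0 to 52 falls from 32 weeks to 0. The visit schedule and the action rules stay as they are. Week 56 is not changed by this edit.

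If the device has already been running with the shorter reference period, the study report should state which weeks the worst postbaseline value covers.

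The cost is two table notes and one check of the device settings. The downside is a recall of 8 weeks (Weeks 8 and 16) or 12 weeks (Weeks 28, 40 and 52) instead of 4, with the poorer recall that a longer period may bring.

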2 INTRODUCTION

Psoriasis is a chronic inflammatory skin disorder, characterized primarily by erythematous scaly plaques, that affects up to 3% of the general population. Men and women are equally affected and it can present at any age.^{1,2} Several studies have observed a bimodal distribution of psoriasis onset with the first peak ranging from 15 to 22 years of age, and the second peak ranging from 55 to 60 years of age.^{3,4,5} The most common form of psoriasis (58% to 97% of cases) is plaque psoriasis (psoriasis vulgaris), with less common forms being guttate, pustular, inverse (flexural), and erythrodermic psoriasis. The disease can have a fluctuating relapsing course, with flares that may be induced by factors such as infections, trauma, smoking, and stress.³ Psoriasis can involve skin in any part of the body; particularly disabling is the involvement of specific anatomic regions, such as hands and feet (palmoplantar), face, scalp and nails. Disease severity can be graded by body surface area (BSA) involvement with mild defined as $\leq 10\%$ BSA, and moderate-to-severe as $>10\%$ BSA.⁶ Psoriasis has a profound impact on quality of life and can lead to psychological, social and economic consequences, especially in moderate-to-severe disease. This condition is also associated with an increased risk of depression, occurrence of sleep disturbances, social stigma and decreased work productivity.^{7,8} Commonly associated comorbidities found in psoriasis patients include diabetes mellitus and metabolic syndrome. In patients with more severe forms of the disease, life expectancy is decreased due to an increase of cardiovascular risk.⁹

Treatments include topical preparations, eg, corticosteroids, vitamin D analogues, calcineurin inhibitors, and salicylic acid; phototherapy modalities, including PUVA (psoralens with UVA) and narrow band UVB; and systemic therapies. In moderate-to-severe disease, systemic treatments are usually needed and may include oral agents (retinoids, methotrexate, cyclosporine, and apremilast) or injectables (eg, biologics such as tumor necrosis factor (TNF) inhibitors etanercept, infliximab, and adalimumab) anti-IL-12/23p40 antibody (ustekinumab), IL-17 antagonists (secukinumab, ixekizumab, and brodalumab), and anti-IL-23p19 antibody (guselkumab). Many of these treatments are associated with increased risk of adverse events (AEs) such as hepatotoxicity and neutropenia (methotrexate);¹⁰ nephrotoxicity (cyclosporine);¹¹ depression and weight loss (apremilast);¹² serious infections (cytokine inhibitors);^{13,14,15,16} candidiasis and Crohn's disease (IL-17 antagonists).^{16,17,18}

Although effective therapeutic options are available, under-treatment or nontreatment of psoriasis has been reported in up to half of surveyed patients (based on absence of treatment and/or dissatisfaction with treatment).¹⁹ Many patients with severe disease are still being managed with only topicals,^{4,8} and many patients consider their psoriasis treatment to be inadequate. Accordingly, there remains a need for more effective oral options, when compared with currently available agents, that would increase adherence to treatment.

2.1 Study Rationale

BMS-986165 could be a therapeutic option for the treatment of subjects with moderate-to-severe plaque psoriasis based on results of a recently completed 12-week, randomized, Phase 2, placebo-controlled, parallel-group study with 5 different BMS-986165 treatment arms: 3 mg every

other day (QOD); 3 mg once daily (QD); 3 mg twice daily (BID); 6 mg BID; and 12 mg QD (Study IM011011). Overall, 267 subjects were randomized (44 to 45 subjects per treatment arm) in the Phase 2 study. All BMS-986165 treatment groups, except 3 mg QOD, achieved the primary endpoint of superiority compared with placebo in the proportion of subjects achieving PASI 75 after 12 weeks of treatment. Compared with placebo treatment group, in which 6.7% of the subjects achieved PASI 75 response, 38.6% (P = 0.0003), 68.9% (P < 0.0001), 66.7% (P < 0.0001) and 75% (P < 0.0001) of subjects treated with 3 mg QD, 3 mg BID, 6 mg BID, and 12 mg QD achieved PASI 75, respectively. The PASI 75 responses plateaued at a dose of 3 mg BID. Also, there was a clinically significant proportion of subjects treated with BMS-986165 achieving an sPGA score of 0 or 1 compared with placebo at Week 12. Compared with the placebo treatment group in which 6.7% of the subjects achieved an sPGA score of 0 or 1, 41.5%, 75.6%, 65.9%, and 75% of the subjects treated with 3 mg QD, 3 mg BID, 6 mg BID, and 12 mg QD achieved an sPGA score of 0 or 1, respectively with responses again plateauing at dose of 3 mg BID. The Phase 3 dose selected (6 mg QD) is expected to demonstrate equivalent efficacy to the 3 mg BID dose. [REDACTED]

This Phase 3 study is designed to confirm the efficacy and safety of BMS-986165 6 mg QD in a population of subjects with moderate-to-severe plaque psoriasis.

2.2 Background

[figure not shown]
Tyrosine kinase 2 (TYK2) is a nonreceptor tyrosine kinase associated with receptors for the p40-containing cytokines IL-12 and IL-23, as well as the Type I interferon (IFN) receptor, and is required for the activation of their downstream signaling pathways. TYK2 catalyzes the phosphorylation of the intracellular receptor domains and signal transducer and activator of transcription (STAT) proteins resulting in the activation of STAT-dependent transcription and functional responses specific for these cytokines.^{20,21,22} Because TYK2-dependent cytokines (eg, Type I IFNs, IL-12, IL-23) are distinct from those dependent on closely related Janus kinase (JAK) family members JAK1/JAK3 (eg, IL-2, IL-15, IL-7) or JAK2 (eg, erythropoietin, thrombopoietin, GM-CSF), a TYK2 inhibitor would be expected to have a highly differentiated profile from inhibitors of other JAK family kinases. TYK2 dependent pathways and the cytokine networks they modulate (eg, IL-23/IL-17, IFN α) have been implicated in the pathophysiology of multiple immune-mediated diseases, including psoriasis, lupus, spondyloarthritides, and Crohn's disease.

[figure not shown]
BMS-986165 is a potent, highly selective, oral small molecule inhibitor of TYK2. A comprehensive in vitro and in vivo characterization of BMS-986165 has been established and supports the development of this compound in humans. Inhibition of TYK2 is expected to provide therapeutic benefit for subjects with psoriasis for multiple reasons: 1) Many of the pathways in the TYK2 signaling cascade (IL-23 and the downstream mediators IL-17 and IL-22; IFN α) have been implicated in pathogenesis of psoriasis.⁷ 2) Biologic agents targeting the IL-17, IL-23p19, and IL-12/23 p40 pathways have been approved for and are highly efficacious in the treatment of psoriasis. [REDACTED]

2.2.1 Early Clinical Development

The clinical data available to date supporting the safety, pharmacokinetics (PK) and pharmacodynamics (PD) of BMS-986165 are from 5 completed Phase 1 studies in healthy subjects (IM011002, IM011015, IM011016, IM011031, and IM011039) and 1 completed Phase 2 study in adult subjects with moderate-to-severe plaque psoriasis (IM011011).

Overall, BMS-986165 has been generally well tolerated across all studies, and no safety issues have been identified to limit the investigation of the dose of BMS-986165 up to 12 mg QD in further clinical studies. A detailed description of the chemistry, pharmacology, efficacy, and safety of BMS-986165 is provided in the Investigator Brochure (IB).

3 OBJECTIVES AND ENDPOINTS

Table 4: Objectives and Endpoints

Objectives	Endpoints
Primary	

Assess whether BMS-986165 is superior to placebo at Week 16 in the treatment of subjects with moderate-to-severe plaque psoriasis	
static Physician Global Assessment (sPGA) 0/1 responsePsoriasis Area and Severity Index (PASI) 75 response (defined as a 75% improvement in PASI score from baseline)
Secondary [REDACTED]	

Assess whether BMS-986165 is superior to placebo over the first 16 weeks of treatment	
sPGA 0/1 responsePASI 90 responsesPGA 0 responsePASI 100 response
[REDACTED]	

Assess whether BMS-986165 is superior to placebo in nail psoriasis through Week 16 in those subjects who have baseline Physician's Global Assessment of Fingernail Psoriasis (PGA-F) score ≥ 3Assess whether BMS-986165 is superior to placebo in palmoplantar psoriasis through Week 16 in those subjects who have baseline palmoplantar Physician's Global Assessment (pp-PGA) score ≥ 3	
PGA-F 0/1pp-PGA 0/1 response

Table 4: Objectives and Endpoints

Objectives	Endpoints

Evaluate improvement in patient reported outcomes for BMS-986165 compared with placebo through Week 16	
Change from baseline in Psoriasis Symptoms and Signs Diary (PSSD) symptom scorePSSD symptom score of 0 (among subjects with a baseline PSSD symptom score ≥ 1)DLQI 0/1 (among subjects with a baseline DLQI score ≥ 2)

